8.5.2. EQ-5D

EQ-5D is a standardized measure of health status developed by the EuroQol Group in order to provide a simple, generic measure of health for clinical and economic appraisal. Analysis of the EQ-5D data will be performed for the PRO (3rd line+) set.

The EQ-5D consists of two parts, the EQ-5D descriptive system and the EQ Visual Analogue Scale (EQ VAS).

EQ-5D Descriptive System

The EQ-5D descriptive system comprises 5 dimensions (mobility, self-care, usual activities, pain/discomfort, anxiety/depression). Each dimension has 5 levels (no problems, slight problems, moderate problems, severe problems, and extreme problems). The respondent is asked to indicate his/her health state or placing a cross in the box against the most appropriate level within each of the 5 dimensions. This decision results in a 1-digit number expressing the level selected for that dimension. The user guide emphasizes that the numerals 1-5 for each level have no arithmetic properties and should not be used as a cardinal score. Ambiguous item values (e.g. 2 levels are ticked for a single dimension) will be treated as missing values.

For the 5 dimensions within the descriptive, at each assessment point, the number and percentage of patients responding in each of the 5 levels will be presented in a table as well as displayed by treatment arm. The number of missing responses will also be displayed. The response profile for

each of the 5 dimensions will be compared between treatment arms over time using generalized estimating equations (GEE). The marginal model will take the form

$$E[Log[P(X \le j)]] = \beta_{0j} + T \cdot \beta_T + V \cdot \beta_V + T \cdot V \cdot \beta_{TV}$$

where $E[\cdot]$ denotes expectation, X is one of the 5 dimensions, j = 1, ..., 5 is the level of the dimension, $P(X \le j)$ denotes the probability a patient's response is $\le j$, β_{0j} is the intercept term associated with level j = 1, ..., 5, T = 0, 1 is the treatment arm indicator, V = 0, 1, ..., v is the visit indicator, β_T are the regression parameters associated with treatment arm level $T = 0, 1, \beta_V$ are the regression parameters associated with visit V = 0, 1, ..., v and β_{PAF} the regression parameters associated with visit V = 0, 1, ..., v and β_{PAF} the regression parameters associated with treatment arm T and visit . V

Results will be displayed as well as presented in a table, in terms of the overall odds ratio for balixafortide + eribulin vs eribulin monotherapy along with the associated 95% CI and 2-sided p-value. Odds ratios by visit will be displayed also.

EQ VAS

The EQ VAS records the patient's self-rated health visual analogue scale with endpoints labelled 'the best health you can imagine' and 'the worst health you can imagine'. The patient is asked 'mark an X on the scale to indicate how your health is TODAY' and then to 'write the number you marked on the scale in the box below'. There will be no programming checks for a discrepancy between where the patient has placed the X and the number they have written in the box, the number in the box is the only value available on the database and to be used for analysis.

EQ VAS scores will be analyzed across visits using an MMRM approach in the same manner as described in Section 8.5.1 for the EORTC-QLQ-C30.

8.5.3. FACT-B

The FACT-B (version 4) is a self-administered questionnaire designed for patients suffering from breast cancer; FACT-B is a breast cancer subscale added to the Functional Assessment for Cancer Therapy -General (FACT-G). It consists of 37 questions grouped into 5 subscales being:

- Physical well-being (7 questions GP1 to GP7, min score=0, max score=28)
- Social/family well-being (7 questions GS1 to GS7, min score=0, max score=28)
- Emotional well-being (6 questions GE1 to GE6, min score=0, max score=24)
- Functional well-being (7 questions GF1 to GF7, min score=0, max score=28)
- Breast subscale (10 questions B1 to B9 and P2, min score=0, max score=40)

All questions are presented with answers on a five-point (0 to 4) Likert scale. As displayed in Appendix 14.4, subscale scores are calculated by first transforming all question scores within a subscale to have the same direction such that the higher the score, the better the QOL, and then summing the resulting scores. If more than 50% of questions are unanswered within a subscale at a particular timepoint, the value for the subscale will be set to missing. If less than 50% of questions are unanswered, the sum of the scores for the answered questions will be taken and scaled up in relation to the number of questions answered or not in the scale. The subscale scores will be combined as follows:

FACT-G total score: PWB score + SWB score + EWB score + FWB score

FACT-B total score: PWB score + SWB score + EWB score + FWB score + BCS score

No imputation will be done if any of the subscores is missing.

Analysis of the FACT-B data will be performed in the PRO set. The 5 subscale scores along with the FACT-G score and FACT-B total score will be summarized by treatment arm at each assessment point using mean, median, standard deviation, min, max and N.

Each of the subscale scores together with the FACT-G score, FACT-B total score will be analyzed over time using an MMRM approach in the same manner as described for the EORTC-QLQ-C30.

8.5.4. Relationship between biomarkers and clinical outcomes

Relation between biomarkers and clinical outcome will be treated in a separate analysis plan.

8.5.5. Response in patient who continue study treatment despite progression

Response in patients who continue study treatment despite progression will be assessed according to iRECIST (2017) by Investigator. A summary table of counts and percentage of patients experiencing each of CR or PR measured at an assessment date later than PD, by visit will be presented by treatment arm. Analyses on patients who continue study treatment after the progression will be descriptive only because these patients did not go through a second randomization process and can be affected by selection bias.

8.5.6. Baseline Tumor Samples

Archival Tumor Tissue and Fresh Tumor Biopsy information will be listed for the ITT (3rd line+) set.

9. Safety Analysis

Safety data will be assessed in the 3rd line+ and overall (2nd line+) populations. Safety data collected in this study includes AEs, serious adverse events (SAEs), clinical laboratory tests, vital signs, physical examination, electrocardiogram, and other safety data including pregnancy during exposure and medication errors. To maximize the ability to discern safety signals, safety and AE data will be summarized on the Safety and Safety (3rd line+) sets, i.e. the overall and 3rd line+ population and will be presented for balixafortide + eribulin and eribulin monotherapy treated patients. All safety data will be presented in data listings.

9.1. Adverse Events

Adverse events will be coded by SOC and preferred term using the latest MedDRA dictionary. Adverse event severity will be based on NCI CTCAE Grade (version 5.0).

All AEs reported from the first dose of study treatment (Cycle 1 Day 1 for balixafortide + eribulin or Cycle 1 Day 2 for eribulin monotherapy) until 30 days after the last dose of study treatment will be considered as treatment-emergent AEs (TEAEs). A TEAE is an AE that was not present prior to first dose of study treatment but appeared following treatment or was present prior to the start of study treatment but worsened thereafter. An AE that was present prior to the start of study treatment, resolved and then reappeared following first dose of study treatment, is a TEAE. If the start date of an AE is incomplete and cannot be categorized as occurring before or after the first

dose of study treatment, then the AE will be considered as a TEAE. If the start time of the AE is presented, then the AE start date and time will be used to classify the AE as TEAE or not. If the start time is not provided and the AE occurs on the same day of first dose of study treatment, then the AE will be classified as a TEAE.

9.1.1. Incidence of Adverse Events

AE data will be descriptively summarized by treatment arm. The incidence of TEAEs by MedDRA SOC, preferred term, and Investigator attributed relationship (related/not related) to balixafortide and/or eribulin, as relevant, will be summarized. AEs will be summarized in terms of frequency and percentage. For patient level of summaries, patients with multiple occurrences of events of the same preferred terms and SOC will be counted once for each preferred term or SOC (at the highest severity/grade and the closest relationship to study treatment as applicable). The summary tables will be ordered by descending incidence of SOC and by descending incidence of preferred term within each SOC class for all patients.

The following adverse events summaries will be provided:

- TEAEs by System Organ Class and Preferred Term
- TEAEs by System Organ Class and Preferred Term and CTCAE Grade
- Grade 3 or Higher TEAEs by System Organ Class and Preferred Term
- Grade 3 TEAEs by System Organ Class and Preferred Term
- Grade 4 TEAEs by System Organ Class and Preferred Term
- Serious TEAEs by System Organ Class and Preferred Term
- Serious TEAEs by System Organ Class and Preferred Term and CTCAE Grade
- TEAEs Related to Study Treatment by System Organ Class and Preferred Term
- TEAEs Related to Study Treatment by System Organ Class and Preferred Term and CTCAE Grade
- TEAEs Leading to Study Treatment Discontinuation by System Organ Class and Preferred Term
- TEAEs Leading to Study Treatment Discontinuation by System Organ Class and Preferred Term and CTCAE Grade
- TEAEs with fatal outcome by System Organ Class and Preferred Term, being AEs with the outcome 'Death Related to Adverse Event' regardless of the attributed relationship to study treatment
- TEAEs Related to Study treatment with outcome 'Death Related to Adverse Event' by System Organ Class and Preferred Term
- TEAEs of Special Interest by Special Interest Group
- TEAEs of Particular Interest by Particular Interest Group

All adverse events will be presented in a listing. Furthermore, listings will be presented specifically for SAEs, TEAEs leading to study treatment discontinuation and TEAEs leading to death.

In addition, the number of TEAEs leading to first eribulin dose reduction will be summarized by cycle and day of onset, in total and split by treatment arm.

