12.2.1 Sample Size

Assuming a median PFS on eribulin of 3.9 months, to test for a hazard ratio versus balixafortide + eribulin of 0.699 (corresponding to a median PFS of 5.6 months), a total of 346 PFS events are required to provide 90% power at the 1-sided 2.0% alpha level. Equally, 346 PFS events provides 94.6% power for a hazard ratio of 0.674, corresponding to a PFS of 5.8 months. Assuming a 12-month recruitment period (η =2; Carroll, 2009(3)) and a minimum 12-month follow-up period after the last patient is randomized, a total of 384 patients will be recruited. Patients who discontinue from the study will not be replaced.

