4.1. Sample Size

The trial is powered for detecting superiority of balixafortide + eribulin versus eribulin monotherapy for the primary efficacy endpoint of PFS in the 3^{rd} line+ population.

In the trial, patients will be randomized in a 1:1 ratio to the two treatment arms stratified by line of therapy (2nd line versus 3rd line+), hormone receptor status (positive versus negative), prior treatment with CDK 4/6 inhibitor (received a CDK 4/6 inhibitor versus not received a CDK 4/6 inhibitor) and visceral versus non-visceral disease.

The sample size calculations are event-driven. In the 3rd line+ population, approximately 320 patients are required in order that 286 PFS events occur within 24 months of randomizing the first patient. Patients who discontinue from the study will not be replaced.

The sample size calculations were based on the following assumptions:

- Overall 1-sided type I error rate: 0.020;
- In the 3rd line+ population, a median PFS on eribulin monotherapy of 3.9 months vs 5.8 months for balixafortide + eribulin to give a PFS hazard ratio 0.674;
- Power of 90%;
- Assuming a 12-month non-linear recruitment period ($\eta=2$; Carroll, 2009) and a minimum 12-month follow-up period after the last patient is randomized.
- Further, assuming a median OS on eribulin monotherapy of 14.4 months vs 17.4 months for balixafortide + eribulin to give an OS hazard ratio 0.828, a total of 226 deaths are expected in the 3rd line+ population in the final analysis of OS, planned to take place 12 months after the PFS analysis. Note, there is only one formal analysis of PFS to take place once 286 PFS events have accrued. No further formal analyses of PFS are planned.

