9.1.8. Adverse Events of Special and Adverse Events of Particular Interest

Adverse Events of Special Interest (AESI) and Adverse Events of Particular Interest (AEPI) will be identified by the investigator and specified in the eCRF.

The list of AESI is: Hypersensitivity or IRRs (serious), Neutropenia (serious), Neutropenic infections, Febrile neutropenia, Renal impairment.

The list of AEPI is: Thrombocytopenia, Peripheral neuropathy, Hepatic impairment, QTc prolongation, Hypersensitivity/IRRs, Neutropenia (serious), Neutropenic infections, Febrile neutropenia and Renal impairment.

The number and percent of patients reporting an AESI or an AEPI will be summarized by treatment arm, MedDRA SOC and Preferred term. All AESI categories will be summarized, while only the following categories will be summarized for AEPI: Hypersensitivity/IRRs, Thrombocytopenia, QTc prolongation, Peripheral neuropathy and Hepatic impairment.

Number of patients reporting at least one event of Hypersensitivity/IRR, Neutropenia (serious) or Febrile neutropenia will also be summarized by maximum severity (Grade 1 to 5) and treatment arm.

The number of patients reporting Neutropenic infections will be summarized by treatment arm and maximum severity (Grade 1 to 5). This table will only be populated when at minimum 4 patients reported at least 1 event of Neutropenic infection and the number of such patients is more than 1% of the Safety population.

The number of Colony Stimulating Factor (CSP) medications will be summarized for all patients experiencing Neutropenia events.

The number of Hypersensitivity/IRRs and Neutropenia (serious) will be summarized by cycle, day of onset, in total and split by treatment arm. The number of all Hypersensitivity/IRR will also be summarized in terms of the event intensity allowing for multiple reactions within a patient total; the latter will be achieved by means of a Negative Binomial analysis with a fixed effect term for randomized treatment and time exposed to randomized treatment as the offset. The rate ratio and the corresponding 95% confidence interval will be obtained based on the Wald approach using the log as link function.

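### The general TEAE tables give crude percentages only, so if PFS is longer on the combination as planned, events that accrue over treatment can show a spurious excess of about 2 to 9 points

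*SAP*

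**What the plan says.** SAP 9.1.1 lists the general TEAE tables: any TEAE, Grade 3 or higher, serious, related, leading to discontinuation, and fatal. They are descriptive, by arm, with each patient counted once per term, and "AEs will be summarized in terms of frequency and percentage". None uses patient-time as a denominator.

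The counting window is set elsewhere. Protocol 3.3 continues treatment until RECIST progression unless toxicity, death, withdrawal or loss to follow-up comes first. SAP 9.1 counts TEAEs from the first dose to 30 days after the last. SAP 7.3.1 tabulates exposure separately, and Protocol 12.4.1 leaves by-cycle AE summaries optional.

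The design assumes "a median PFS on eribulin monotherapy of 3.9 months vs 5.8 months for balixafortide + eribulin" in the 3rd line+ population (SAP 4.1). For the Overall Population, Protocol 12.2.1 assumes a hazard ratio "of 0.699 (corresponding to a median PFS of 5.6 months), a total of 346 PFS events are required".

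SAP 9.1.8 does use time-based methods for the named categories. All hypersensitivity/IRR events get a negative binomial rate ratio with "time exposed to randomized treatment as the offset". The AESIs and AEPIs get Kaplan-Meier time to onset by arm. Serious and febrile neutropenia get a probability-of-being-in-event analysis.

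**The concern.** A longer window gives a patient more opportunity to have at least one event. If the combination delays progression as the design assumes, its patients are watched for TEAEs for longer. An identical event rate in the two arms can then appear as a higher percentage on the combination.

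Comparing safety with eribulin alone is a secondary objective (SAP 2.2), and the tables in SAP 9.1.1 are the ones most readers will use for it. At stake is the reading of the benefit-risk balance. No formal error rate is involved, because no between-arm test is planned on these tables.

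**Working it through.** **Inputs.** Median PFS 3.9 versus 5.8 months, hazard ratio 0.674, 286 events, 90% power (SAP 4.1). Alpha is given as "Overall 1-sided type I error rate: 0.020". Overall Population: 5.6 months, hazard ratio 0.699, 346 events (Protocol 12.2.1). The TEAE tail is w = 30/30.4375 = 0.986 months. AE hazards are assumed over a range, because the documents state no planning AE rates.

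**Step 1: reproduce the plan's figure.** Schoenfeld events at 1:1 are 4(z₀.₉₈ + z₀.₉₀)²/(ln HR)². With HR 0.674: 4(2.054 + 1.282)²/(ln 0.674)² = 285.9, so 286 as stated. With HR 0.699 the formula gives 347 against 346 stated, which is close enough.

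**Step 2: length of the window.** Take exponential time on treatment with the PFS medians, so the mean is m = median/ln 2. This gives 5.63 months (eribulin), 8.37 (combination, 3rd line+) and 8.08 (combination, overall).
- Ratio of medians: 5.8/3.9 = 1.49; 5.6/3.9 = 1.44.
- Ratio of mean windows, tail included: (8.37 + 0.99)/(5.63 + 0.99) = 1.41; (8.08 + 0.99)/(5.63 + 0.99) = 1.37.

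Now add an assumed equal hazard d of stopping for reasons other than progression, so the mean is 1/(ln 2/median + d), in 3rd line+:
- d = 0.03 per month: (6.69 + 0.99)/(4.81 + 0.99) = 1.32.
- d = 0.06 per month: (5.57 + 0.99)/(4.21 + 0.99) = 1.26.

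**Step 3: crude incidence with equal constant hazards.** For a first-event hazard λ in both arms, P = 1 − exp(−λw)/(1 + λm). Setting λ to give a chosen percentage on eribulin:

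| λ per month | Eribulin | Combination, 3rd line+ | Excess (points) |
|---|---|---|---|
| 0.0079 | 5% | 6.9% | 1.9 |
| 0.0166 | 10% | 13.6% | 3.6 |
| 0.0366 | 20% | 26.1% | 6.1 |
| 0.0613 | 30% | 37.8% | 7.8 |
| 0.1338 | 50% | 58.7% | 8.7 |
| 0.2743 | 70% | 76.8% | 6.8 |
| 0.7073 | 90% | 92.8% | 2.8 |

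The 30% row in full: exp(−0.0613 × 0.986) = 0.941; 1 − 0.941/(1 + 0.0613 × 5.63) = 0.300; 1 − 0.941/(1 + 0.0613 × 8.37) = 0.378. With the overall median of 5.6 months it is 37.0%. With d = 0.03 and 0.06, 30% becomes 36.2% and 35.1%.

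**Step 4: events that occur only early.** Let the hazard act only in the first 42 days (two cycles), so time at risk is the smaller of T + w and 42 days. An event seen in 30% on eribulin is then seen in 30.1% on the combination, so the crude percentage is close to correct.

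**Step 5: what a simple rate does in that case.** Mean time to first event or end of window is 4.81 versus 6.72 months. First-event rates are 0.300/4.81 = 6.2 and 0.301/6.72 = 4.5 per 100 patient-months, a ratio of 0.72. The true risks are equal, so here the rate misleads in favour of the combination.

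**The case against.** The strongest reply is that the plan already handles time where it matters most. SAP 9.1.8 covers IRR, neutropenia, febrile neutropenia, neutropenic infections, thrombocytopenia, neuropathy, hepatic impairment, QTc prolongation and renal impairment with Kaplan-Meier time to onset. Serious neutropenia and IRR are also shown by cycle and day of onset. A reader who saw only the IRR offset might infer that nothing else accounts for time; that is not so. What remains is that these methods stop at the named categories. The Kaplan-Meier output is a median or 25th percentile per arm with no contrast specified. Its censoring (death, last visit or new anti-cancer therapy) also differs from the TEAE window.

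A second reply is that the documents never say how long treatment will last in either arm. A reader might infer from the PFS medians that the plan expects about 50% longer treatment. That goes too far: toxicity and withdrawal shorten treatment, continuation past progression is allowed, and the fixed 30-day tail dilutes the ratio. The only duration figure is the Phase 1 median of 105 days (3.45 months), against a median PFS of 4.5 months (Protocol 2.5.1). This stands, and it is why the effect is stated conditionally.

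Third, many toxicities here come early. Protocol 9.2.6.3 places most earlier hypersensitivity events at first administration, and Protocol 9.2.6.4 gives a mean time to neutrophil nadir of 13 days. For such events the artefact nearly vanishes, and a rate per patient-month would create the opposite one. This stands too, and it shapes the fix.

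Finally, the tables are descriptive and exposure is tabulated, so a careful reader can see unequal durations. That limits the consequence but does not supply the adjusted figure.

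**Conclusion.** The point holds as a modest gap in presentation. The overall TEAE categories have no time-at-risk companion. If the PFS assumption is met and drives treatment duration, the mean TEAE window would be about 37–41% longer on the combination, or about 26–32% in 3rd line+ with 3–6% monthly stops for other reasons. Under an equal constant hazard, the false excess is about 2 to 9 points, largest for events of middling frequency. It is almost nil for events confined to the first two cycles.

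This rests on exponential treatment times, PFS as a stand-in for treatment duration, and assumed AE hazards. It would be too strong to infer that equal toxicity will in general look like an excess: that depends on events accruing throughout treatment. Nor do the documents give any figure to support the mirror-image claim that early stopping would mask added toxicity, so no weight is put on it.

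**What to change.** Keep the crude percentages. For any TEAE, Grade 3 or higher, serious, related, and leading to discontinuation, add two summaries by arm:

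- **(a)** Patients with a first event per 100 patient-months at risk, with time counted to the first event or to last dose + 30 days, and the rate difference with a 95% CI.
- **(b)** A mandatory fixed-window or by-cycle summary, or cumulative incidence. This is needed because rates per patient-month dilute early-onset events in the longer-exposed arm (step 5 of the working).

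There is no need to extend this to every system organ class and preferred term. A footnote should say that the rates in (a) assume a roughly constant hazard.

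The cost is a few supplementary tables and that caveat. First-dose, last-dose and event-onset dates are already used in SAP 7.3.1 and 9.1.8, so no new data are required.

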9.1.2. Severity of Adverse Event

The severity that will be presented represents the most extreme severity captured on the eCRF page. The possible severities are measured on the CTCAE scale which goes from 1 to 5 where 1='mild', 2='moderate', 3='severe', 4='life-threatening' and 5='fatal'. Treatment-emergent AEs with a missing severity will be summarized in tables as Grade 3 but will be presented in the data listing with a missing severity.

In the TEAE severity table, if a patient reported multiple occurrences of the same TEAE, only the most severe will be presented. A further summary table of only those TEAEs with CTCAE grade 3 or higher will also be presented.

